## C. Study Design and Research Methods

Potentially eligible subjects will be screened during routine clinic visits or over the telephone. Potentially eligible and interested subjects will return for informed consent and a screening/baseline visit. No research procedures will occur prior to consent, including the MOCA.

After obtaining informed consent, participants will undergo a graded exercise test to screen for potential underlying cardiovascular disease. V02 peak will be measured at this time to develop the exercise prescription. All participants will begin with a low intensity lead-in for 1-2 weeks, then advance to a moderate intensity exercise during first 12 weeks. Randomization to continue on moderate versus advance to high intensity will occur at week 13.

**1. Consent & baseline visit.** After obtaining consent, the participant will be evaluated

-After obtaining consent, the participant will be evaluated by

- medical history, physical examination including vital signs
- Montreal Cognitive Assessment (MOCA)
- Resting BP, 12-lead resting ECG, and then a graded exercise test (GXT) administered by research personnel and a clinician experienced in exercise stress testing of older adults ([name]) to screen out volunteers with evidence of ischemic heart disease, serious arrhythmias, or abnormal HR/BP responses to exercise. Briefly, the test will begin at a comfortable walking speed and 0% elevation; speed will be maintained and the grade increased by 2% every 2 min, until the participant reaches 85% of age-predicted maximal heart rate or the test is otherwise terminated. The absolute and relative indicators for terminating an exercise test that are recommended by the American College of Sports Medicine (ACSM) will be employed.
- Baseline physical function assessments will be administered.

**2. Procedure visit #1 (within 14 days of visit #1).** All participants will arrive between 7:30-8am for:

- DXA scan
- Vital signs
- Anthropometrics (waist/hip circumference)
- Blood draw (fasting)
- 36 (up to 46, if needed to ensure 36 paired biopsy samples) volunteer participants (18 HIV+/18 HIV-) will have a muscle biopsy
  - If muscle biopsy at the end of the study cannot be done (patient refuses, change in medications, etc), then the number of biopsies will increase to a maximum of 46 in order to ensure each group has at least 18 paired (entry/completion) biopsy samples.
- Questionnaires

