## **F. Data Analysis Plan:**

### **Statistical Considerations**

Sample Size Calculations: The primary outcome for sample size calculations is change from baseline in chair rise pace. We assume a change from baseline of 1.5 (SD=1.54) seconds or larger, based on differences observed by fall history [85]: Sample sizes of 36/group will yield an estimate of 29 patients per group at week 16 (~20% dropout). 29 subjects per group achieves over 80% power to detect a between group difference of 1.5 seconds with a significance level of 0.05 and the standard deviation conservatively estimated at 2.0 seconds[110] using a two-sided two-sample equal variance t-test.

Matching and Randomization: Enrollment in the uninfected arm will be constrained to lag behind HIV-enrollments. Upon the enrollment of every 5th HIV-infected patient, HIV-uninfected enrollment will be evaluated and recruiting goals updated to ensure a similar age (<60; >=60), gender, BMI, and smoking

distribution. Given the smaller proportion of women in the HIV-infected population, we plan to enroll fewer women. The randomization will be blocked by gender and exercise intensity to ensure balance according to the following scheme:

Exercise Intensity	Moderate (N=36)		High (N=36)	
HIV-Infected (N=36)	Men:	15	Men:	15
	Women:	3	Women:	3
Controls (N=36)	Men:	15	Men:	15
	Women:	3	Women:	3

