**Analysis Plan:** Given repeated measurements over time, a linear mixed effects model will be used with change from week 0 as the primary outcome. The inclusion of additional time points will provide additional power. Groups defined by HIV-status (Exercise Intensity) will be evaluated. The baseline value and a group and time interaction term will be included as model predictors. The primary analysis will be intent to treat. Baseline (week 0) characteristics will be compared between groups prior to comparisons of endpoints, with log transformation for normality, as appropriate. The primary analysis will consider adjusting for age, smoking, exercise intensity (HIV-status) and body mass index (BMI); although if matching and/or balance by group is achieved, they may be precision variables, but they cannot be confounders. Finally, given the potential for non-ignorable dropout, we will accommodate dropout in the analysis of functional measures using a semi-parametric varying-coefficient model approach [150]. The primary analyses will assume that the slope beyond dropout is linear with sensitivity analyses utilizing a slope is attenuated by 50% and a zero slope beyond dropout, the latter being similar to a last value carried forward. Additionally a sensitivity analysis using only data from study completers will be conducted.

Change in IGF-I mRNA will be a primary outcome in the subset of participants undergoing muscle biopsy.

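### Gender blocks the intensity randomisation and guides HIV-negative recruitment, yet it is the only one of these design factors missing from the model terms

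*Combined protocol and SAP*

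**What the plan says.** All the relevant text is in section IV of the combined protocol and SAP, mostly in F (Data Analysis Plan, Statistical Considerations).

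- **Timing of randomisation** (C, Study Design and Research Methods): "Randomization to continue on moderate versus advance to high intensity will occur at week 13".
- **Blocking** (Matching and Randomization): "The randomization will be blocked by gender and exercise intensity to ensure balance according to the following scheme". The table that follows sets 15 men and 3 women in each of the four HIV-by-intensity cells. That is 6 women in each intensity arm and 12 of 72 overall. The small number is deliberate: "Given the smaller proportion of women in the HIV-infected population, we plan to enroll fewer women".
- **Matching of the HIV-negative group** (same paragraph): after every fifth HIV-infected enrolment, "HIV-uninfected enrollment will be evaluated and recruiting goals updated to ensure a similar age (<60; >=60), gender, BMI, and smoking" distribution.
- **Model** (Analysis Plan): "Groups defined by HIV-status (Exercise Intensity) will be evaluated", which we read as one model for HIV status and one for intensity. "The baseline value and a group and time interaction term will be included as model predictors". For the rest, "The primary analysis will consider adjusting for age, smoking, exercise intensity (HIV-status) and body mass index (BMI".

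Gender is in neither list of model terms, and no gender-stratified or gender-adjusted analysis is described elsewhere. The background (section II) states that quantitative responses to exercise vary by gender, among other factors.

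**The concern.** Four factors guide recruitment of the HIV-negative group: age, gender, BMI and smoking. Two strata shape the intensity allocation: gender and HIV status. All of these except gender are carried into the model paragraph, so the gap looks like an oversight. The authors also expect gender to affect the response being measured.

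The two contrasts are affected differently.

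- **Intensity (randomised).** Blocking on gender removes the between-gender component from the true sampling variance of the arm difference. A model without gender still counts that component as residual noise. The reported standard error is then larger than the design warrants, and some precision is given away.
- **HIV status (not randomised).** Gender balance depends on recruitment goals being met and on similar dropout. If balance fails, gender can confound, and the list of possible adjusters does not include it.

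**Working it through.** **1. The plan's own figure.** "Sample sizes of 36/group will yield an estimate of 29 patients per group at week 16 (~20% dropout"): 36 × 0.8 = 28.8, about 29. With a difference of 1.5 s, SD 2.0 s, two-sided alpha 0.05 and an equal-variance t-test, power at 29 per group is 80.1% (noncentral t). The statement of over 80% reproduces, with almost no slack.

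**2. Inputs for the gender effect.** Share of women p = 12/72 = 1/6, from the scheme table, so p(1 − p) = 1/6 × 5/6 = 0.139. The gender difference in mean change, d, is not in the documents. It is assumed to be 0.25 to 1.0 in units of the total SD, and to be what remains after adjustment for baseline. On an SD of 2.0 s that is 0.5 to 2.0 s.

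**3. Formulas.** Variance explained by gender: R² = p(1 − p)d². Residual SD with gender in the model: 2.0 × √(1 − R²). Narrowing of the standard error: 1 − √(1 − R²). Power is the t-test calculation of step 1 with the residual SD in place of 2.0. Type I error comes from 40,000 simulated trials per setting, with 36 per arm and 6 women in each arm.

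| d (SD) | R² | Residual SD (s) | SE narrower by | Power, 29 per group, with gender | Type I error without gender | with gender |
|---|---|---|---|---|---|---|
| 0.25 | 0.9% | 1.991 | 0.4% | 80.5% | 0.049 | 0.050 |
| 0.5 | 3.5% | 1.965 | 1.8% | 81.5% | 0.046 | 0.050 |
| 0.8 | 8.9% | 1.909 | 4.5% | 83.7% | 0.039 | 0.049 |
| 1.0 | 13.9% | 1.856 | 7.2% | 85.6% | 0.036 | 0.050 |

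For d = 1.0: R² = 0.139 × 1 = 0.139; √(1 − 0.139) = 0.928; 1 − 0.928 = 7.2%. Seen from the other side, the standard error without gender is 1/0.928 = 1.078 times the one with it.

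**4. How much of the power gain comes from the model term.** The 80.1% is a formula value that takes no credit for blocking. In the simulation both analyses are applied to the same blocked trials at 36 per arm with a true difference of 1.5 s. Power without and with gender is 88.2% and 88.3% at d = 0.25, and 89.9% and 92.3% at d = 1.0. The gain from the term itself is therefore about 0.2 to 2.4 points. The rest of the gain in the table comes from blocking, whichever model is fitted.

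**5. HIV contrast.** If one group has one more woman among 29 than the other, the unadjusted difference shifts by (1/29) × gender difference. That is 0.034 × 0.5 s = 0.02 s up to 0.034 × 2.0 s = 0.07 s per woman of imbalance, against the 1.5 s the trial is sized for.

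**The case against.** The strongest reply is that this is small. At 0.25 SD the standard error changes by 0.4%, and the upper end of the range is demanding: 1.0 SD is a gender difference in change of 2.0 s, more than the 1.5 s target. The baseline value is a committed predictor and will already absorb whatever part of a gender difference runs through starting function. Only participants still on study at week 13 are randomised, so the cell numbers in the table are targets and balance in the analysed data will be approximate. The plan itself recognises that a covariate balanced between groups can only sharpen the estimate. All of this stands. It limits the size of the point without removing the omission.

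Three stronger readings are tempting, and the documents do not support them.

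- **That the analysis ignores the randomisation strata altogether.** HIV status, the other stratum in the table, is listed for the intensity contrast through the parenthesis in the covariate sentence. Only gender is missing.
- **That the test of intensity is invalid.** There is no bias, and the type I error is at or below 0.05 throughout. The error is on the conservative side.
- **That intensity could end up unbalanced within HIV status because the blocking sentence does not name HIV status.** The sentence refers directly to the scheme, and the table fixes 18 moderate and 18 high in each HIV group. Sentence and table form one specification. What remains is loose wording: intensity is the arm being assigned, so it is not a blocking factor.

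**Conclusion.** The omission is real and worth correcting, but minor in size. For the intensity contrast it costs a little precision and makes the test mildly conservative, to the extent shown in the table. Those figures rest on three assumptions: a gender difference of 0.25 to 1.0 SD that survives baseline adjustment, the planned one-sixth share of women, and a single-endpoint comparison standing in for the repeated-measures model. The lower half of the range is close to negligible.

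For the HIV contrast there is no problem if gender matching is achieved and maintained. If it is not, gender becomes a possible confounder with no place in the prespecified model. At the assumed differences the distortion would be small unless the imbalance ran to several women.

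A related weakness is that HIV status, although listed for the intensity contrast, is only to be considered, so adjustment for that stratum is not firmly prespecified either.

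**What to change.** In the Analysis Plan, make gender and HIV status fixed terms in the intensity model, and make gender a fixed term in the HIV-status model, none of them optional. In Matching and Randomization, reword the blocking sentence to say that allocation to intensity is stratified by HIV status and gender, as the table shows.

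The cost is a few words in two paragraphs and one degree of freedom for gender in each model. Sample size, recruitment and trial conduct do not change.

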#### **B. Description of Population to be Enrolled:**

Participants will be sedentary men and women between the ages of 50 and 75 years (*performing < 2 days/week of 30 minutes of CEx or REx during the prior 6 mo*). HIV+ subjects will initially be recruited from the University of Colorado Infectious Diseases Group Practice which provides care for approximately 1700 HIV+ adults, with 528 patients aged 50-59, 170 patients aged 60-69, 25 patients aged 70-79. Subjects will be on effective ART for a minimum of 2 years with HIV-1 viral load primarily below the limit of detection with no HIV RNA >200 copies/mL. Recruitment of HIV- subjects will first target high risk HIV- partners, friends, or family members of HIV+ subjects, current research participants of IMAGE (Investigations in Metabolism, Aging, Gender and Exercise) research group, the Internal Medicine Clinic, and the Family Medicine Clinic. Inclusion and exclusion criteria were selected to enroll the most appropriate study population while maximizing the generalizability of the findings.

- Inclusion:
  - Between the ages of 50-75 years at study entry
  - HIV+ subjects must be on an ART regimen (change in regimen permitted for preference/tolerability but not for virologic failure) for a minimum of 2 years, with a viral load < 200 during that 2 year period
    - Initial recruitment will target those on ART for at least 5 years; this will be removed as needed to achieve target sample size
  - Sedentary (< 2 days/week of CEx and/or REx over the prior 6 months)
  - CD4 T-cell count greater than 200 cells/mm^3
  - All participants must be able to perform activities of daily living without assistance, and ambulate independently.
  - BMI  $\geq$  20 and <40 (initial goal, will expand if difficulties recruiting)
  - Among females, must be post-menopausal (no menses for >12 months, or if prior hysterectomy, FSH >30 IU/l)
- Exclusion criteria:
  - Due to interaction with the GH/IGF-I axis, persons **with diabetes with a hemoglobin A1c >7%, on insulin, on GLP-1 analog, or DPP IV inhibitors. Well-controlled diabetics on other oral medications with hemoglobin A1c of 7.5 or less are eligible.**
  - Persons on growth hormone or growth hormone axis therapy (i.e., tesamorelin) will be excluded.
  - Post-menopausal use of stable doses of estrogen/progesterone (at least 3 months) will be permitted.

- Persons on intramuscular testosterone will be excluded; stable doses of patches or gel will be permitted

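### For the non-randomised HIV comparison, coarse group matching cannot rule out confounding, so covariate adjustment should be pre-specified rather than optional

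*Combined protocol and SAP*

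**What the plan says.** Section IV.F, Matching and Randomization, describes how the uninfected group is built. Its enrolment lags behind the infected group and is steered: "Upon the enrollment of every 5th HIV-infected patient, HIV-uninfected enrollment will be evaluated", with "recruiting goals updated to ensure a similar age (<60; >=60), gender, BMI, and smoking" distributions between groups. This is frequency matching through recruitment targets, not pair matching. Age is the only variable with stated categories.

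The Analysis Plan in the same section uses one mixed model description for both contrasts, HIV status and exercise intensity. The terms it fixes are these: "The baseline value and a group and time interaction term will be included as model predictors". Everything else is discretionary: "The primary analysis will consider adjusting for age, smoking, exercise intensity (HIV-status) and body mass index (BMI"). It then adds that, on condition that the groups have been matched and/or balanced, "they may be precision variables, but they cannot be confounders". No criterion is given for matching or balance being achieved. The plan does not say whether age would enter as continuous or banded, or what would decide whether to adjust. Baseline characteristics are to be compared between groups before endpoints.

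Only exercise intensity is randomised, at week 13 (section IV.C, Randomization/Week 13 visit). The HIV comparison is Hypothesis 1a. Section IV.B recruits the infected group initially from one HIV clinic. It recruits the uninfected group from partners, friends and family of participants, a metabolism, ageing and exercise research group, and two general clinics.

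**The concern.** Randomisation makes baseline variables independent of treatment in expectation. Recruiting to targets does not do this for HIV status. It makes the proportions in the matched categories similar, but leaves open the distribution inside a category and the joint distribution across variables. With an age range of 50 to 75, the two bands are about 10 and 15 years wide. The condition in the plan is joined by and/or, so meeting the band targets alone would be enough to declare that age cannot confound.

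The protocol itself treats these variables as related to exercise response. Its Background says exercise-stimulated growth hormone release weakens with age and obesity, that the muscle IGF-I response is blunted with ageing, and that smoking may impede the cardiorespiratory response. Section IV.G would read a smaller chair-rise gain in the HIV group as confirmation that something interferes with the response to exercise. A residual difference in age, BMI or smoking is a competing explanation. As written, the choice to adjust can be made after the baseline comparison has been seen.

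**Working it through.** **Inputs from the plan.** 36 per group, about 20% dropout, 29 evaluable per group, difference 1.5 s, SD 2.0 s, two-sided 0.05 (Sample Size Calculations). Age limits 50 to 75 and clinic counts of "528 patients aged 50-59, 170 patients aged 60-69, 25 patients aged 70-79" (section IV.B).

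**Assumptions, not in the documents.** A mean age gap of 3 to 5 years between HIV groups within an age band, with the band proportions identical in both groups. A loss of 0.02 to 0.10 s of chair-rise gain per year of age.

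**Step 1: the plan's own power.** 36 × 0.8 = 28.8, about 29. SE = 2.0 × √(2/29) = 0.525 s. For a 1.5 s difference, power is 80.1% by noncentral t and 81.5% by normal approximation. The stated power of over 80% is reproduced, and there is no sample size error.

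**Step 2: share of the clinic pool aged 60 or over.** (170 + 25)/(528 + 170 + 25) = 195/723 = 27%. Some of the 25 are above the age limit of 75. If none were eligible, the share would be 170/698 = 24%.

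**Step 3: bias in the overall HIV contrast.** Bias = age gap × slope × share of participants in the affected band(s). Within a band it runs from 3 × 0.02 = 0.06 s to 5 × 0.10 = 0.50 s.

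| Where the gap exists | Bias (s) | Fraction of 1.5 s | In units of SE | Type I error, unadjusted test |
|---|---|---|---|---|
| 60 or over only (× 0.27) | 0.016 to 0.135 | 1% to 9% | 0.03 to 0.26 | 5.0% to 5.7% |
| Both bands | 0.06 to 0.50 | 4% to 33% | 0.11 to 0.95 | 5.1% to 15.5% |

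Take an intermediate case of 3 years × 0.10 s/year in both bands. The bias is 0.30 s and the type I error 8.7%. Against a true 1.5 s difference, power is 61% if the bias opposes the effect and 92% if it adds to it.

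**Step 4: which adjustment removes it.** A simulation of 4,000 trials used 29 per group, identical band proportions, ages skewed to opposite ends of each band (mean gap about 3.8 years), a linear slope of 0.10 s/year and no true HIV effect:

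- Unadjusted: bias 0.36 s, rejection 8.8%.
- Adjusted for age band only: bias 0.36 s, rejection 10.5%.
- Adjusted for continuous age: bias about 0 s, rejection 4.8%.

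Adjusting for the matching band therefore does nothing for a gap inside it. Continuous age does, provided the age effect is near linear.

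**The case against.** The strongest reply is that the clause is conditional. If a covariate's full distribution really were balanced between groups, it would not confound a linear comparison, and the sentence would be right. That stands. The weakness is that the condition is undefined and that two-band matching can satisfy it.

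A reader might infer that the plan commits to an unadjusted HIV comparison once the baseline table looks balanced. It does not say so. The covariates are named as candidates, and calling them precision variables is, if anything, a reason to keep them. The baseline chair-rise value is also always in the model. That helps with differences in starting level, but it need not remove an effect of age on the response to training.

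A reader might also take the clinic counts as evidence that the groups will differ in age. They describe only the infected pool, include people over the age limit, and say nothing about the controls. The first-named control source is people close to the infected participants, who may well be of similar age.

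Nor do the documents show that BMI and smoking are matched in broad strata. No categories are stated for them, so the gap is an unstated tolerance. Gender and intensity are a different matter: the allocation scheme sets 15 men and 3 women in every cell and equal intensity arms in each HIV group. If the scheme is met, adjusting for these two is a precision choice and corrects no error.

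**Conclusion.** The point holds for the HIV contrast only. Meeting the matching goals does not justify saying that age, BMI and smoking cannot confound a non-randomised comparison, and adjustment should not be left open. For the randomised intensity contrast the plan's reasoning is acceptable.

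The size is unknown and may be small. The documents give neither an age slope nor an expected age gap. Under the assumptions above, the bias is about 0.02 to 0.14 s if the gap is confined to those aged 60 or over at the clinic's 27% share, and 0.06 to 0.50 s if it exists in both bands. The standard error used for comparison is that of the plan's two-sample calculation, not of the mixed model.

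It would be tempting to conclude that the primary HIV comparison is seriously biased. Larger figures, such as 0.75 s with a type I error of 28.9%, need a 5-year gap in both bands and a slope of 0.15 s/year, and nothing in the documents supports those values. The reason to act is that the premise is wrong for this contrast and the remedy costs almost nothing.

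**What to change.** In the Analysis Plan:

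- Remove the clause on confounders for the HIV contrast, or restrict it explicitly to randomised intensity.
- Pre-specify continuous age, continuous BMI and smoking in the primary HIV model, whatever the baseline comparison shows. Gender and randomised intensity may be added for precision.
- Because the HIV effect is read through a group-by-time term, state whether these covariates also receive a time term.
- Report the unadjusted estimate beside the adjusted one.

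The cost is SAP wording and a few degrees of freedom (about five if gender and intensity are included) from roughly 58 evaluable participants (2 × 29). No new data are needed, since these variables already appear in the matching scheme or in the plan's own list of candidate covariates.
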